Confidentiality will be protected by collecting only information needed to assess study outcomes, minimizing to the fullest extent possible the collection of any information that could directly identify subjects, and maintaining all study information in a secure manner. To help ensure subject privacy and

confidentiality, only a unique study identifier will appear on the data collection form. Any collected patient identifying information corresponding to the unique study identifier will be maintained on a linkage file, store separately from the data. The linkage file will be kept secure, with access limited to designated study personnel. Following data collection subject identifying information will be destroyed three years after closure of the study through institutional shredding and deleting the data. Data access will be limited to study staff. Data and records will be kept locked and secured, with any computer data password protected. No reference to any individual participant will appear in reports, presentations, or publications that may arise from the study.

Data and Safety Monitoring

The principal investigator will be responsible for the overall monitoring of the data and safety of study participants. The principal investigator will be assisted by other members of the study staff.

Reporting of Unanticipated Problems, Adverse Events or Deviations

Any unanticipated problems, serious and unexpected adverse events, deviations or protocol changes will be promptly reported by the principal investigator or designated member of the research team to the IRB and sponsor or appropriate government agency if appropriate.

REFERENCES CITED

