AIM 1: To robustly characterize the relationship between physical performance, functional impairment, and sarcopenia status of community-dwelling older women with UI in up to 100 women.

Hypothesis 1. Functional impairment and sarcopenia will be prevalent among older women seeking care for UI and will negatively correlate with UI severity in a diverse sub-specialty-based clinic population.

Urinary incontinence will be defined as bothersome involuntary leakage of urine at least 2 times/week and characterized by 3 day voiding diary. Physical and functional performance will be measured using the extended Short Physical Performance Battery, a timed 400 meter walk, and Isokinetic dynamometer (Biodex). Sarcopenia status will be determined by the composite of an Appendicular skeletal muscle mass index (ASMI) <5.5 kg/m², usual walk speed <1 m/s, and hand-grip strength ≤ 20.5 kg.

AIM 2: To compare a well-characterized cohort of functionally impaired older incontinent women to a control group of functionally normal older incontinent women to assess the impact of sarcopenia and functional impairment on efficacy of a standardized 6 week PFME prescription for treatment of UI.

Hypothesis 2. Functional impairment and sarcopenia status will be independent predictors of efficacy of PFME therapy in a well-characterized cohort of older women with UI. Specifically, older incontinent women without functional impairment will have greater improvement in UI episodes after PFME therapy in comparison to those with functional impairment. Sarcopenia with functional impairment will be defined as a grip strength <16 kg or gait speed <1 m/s. We expect a 6 week PFME prescription to decrease UI episodes by 50% defined in a 3 day bladder diary and the full 12 weeks to decrease UI episodes even more. Pelvic floor strength will be objectively measured using the PERFECT assessment and perineometer.

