ECT = every contraction timed – Indicates that the above scheme is repeated up to 10 repetitions with each there is a determination of power, endurance and repetitions.

A prescription will be provided for each participant based on their individual PERFECT assessment; typically this details numbers of repetitions, duration of squeezes, and numbers of sets. Based on physical therapy and exercise science literature, 8-12 repetitions of 3-4 sets over 6 weeks increases strength and efficiency of muscle recruitment.[23]

All participants will use a calendar to record daily compliance with PFMEs.

E. UI assessment: UI and pelvic floor symptom assessment will be performed by asking for a history of UI symptoms (years), UI treatment, and number of pads used per day for UI. Participants will complete a 3-day voiding diary to record urinary frequency, urinary urgency and incontinence episodes classified by clinical type (urgency, stress, insensible) along with time of occurrence (day, night).[24] This will be returned during week 2 (baseline), week 6, and week 12. UI symptom impact on daily life will be measured subjectively with the QUID and the Pelvic Floor Impact Questionnaire (PFIQ)-Short Form 7.[25] The Pelvic Floor Distress Inventory (PFDI) short-form 20 will be used to

characterize all pelvic floor symptoms (urinary incontinence, fecal incontinence, voiding dysfunction, overactive bladder, and pelvic organ prolapse).[25]

F. Physical function assessment: Participants will undergo the following assessments:

- **Extended version of the Short Physical Performance Battery (expSPPB).** The expSPPB is a standard and robust predictor for disability that includes progressively more challenging standing balance tasks held for 10-30 seconds each (side-by-side, tandem, and semi-tandem, single leg), 4-meter walk to assess usual gait speed, 4-meter narrow walk test of balance, and five chair-stands test.[26, 27] The timed 4-meter walk will be performed as a surrogate for the 6-meter walk; it is associated with urgency/stress UI and its results are strong predictors of falls and fractures in women.
- **Timed 400 meter walk (min:sec) (22)**
- **Isokinetic dynamometer (Biodex®)** as an objective measure of strength, maximal isokinetic knee extensor strength in the right leg will be measured at speeds of 60 degrees/sec. The left leg will be used if the participant has severe knee pain or a joint replacement in the right knee.

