- Balance will be measured using a **postural sway test**. Center-of-pressure (COP) trajectory data will be collected using an Advanced Mechanical Incorporated (AMTI) AccuSway biomechanics force platform. Four posturographic parameters (maximum antero-posterior and medio-lateral displacement, average sway velocity, and 95% confidence ellipse) and two statistical mechanics measures (stabilogram diffusion analysis and detrended fluctuation analysis) will be calculated to quantify postural sway according to our previously published methods. [30]

G. Comprehensive prospective evaluation for physical function limitations will be assessed with the Pepper Assessment Tool for Disability (PAT-D) and the Mobility Assessment Tool-Short Form (MAT-SF) to measure activities of daily living disability, mobility disability and instrumental activities of daily living disability to assess changes in disability. The MAT-SF is a novel, computerized tool for self-assessment of functional performance designed to reduce bias from factors such as age, gender and body image.[31] [32]

H. Sarcopenia will be determined using the following validated questionnaires and objective physical function measures with standard cut-offs:

- Grip-strength and gait speed will objectively measure weakness.[33]
- The “SARC-F” is a short-form questionnaire validated to identify adults with sarcopenia and who are at risk for adverse outcomes and may benefit from a physical function intervention. [34]
- Whole-body DEXA scans will be used to calculate the appendicular lean muscle mass.[35, 36]

I. Physical activity will be assessed using the Community Healthy Activities Model Program for Seniors (CHAMPS) questionnaire assesses weekly frequency and duration of various physical activities common to older adults to evaluate the efficacy of behavioral interventions aimed at increase levels of physical activity. Caloric expenditure (MET hours/week) will be reported.[8] 'Low activity' will be defined as <6.2 MET-hours/week of activity. Women with 6.3-11.4 MET hr/week will be classified as having low-moderate activity. Since only 23% of incontinent women had >11.4 MET hours/week of physical activity, this level will be defined as high activity.[8] Validated questions will be asked to identify potential barriers to physical activity related to UI symptoms.[37]

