400 meter walk (min:sec)	The 400m walk is a direct measurement of exercise tolerance AND correlates with measured VO ₂ peak.[41]
Isokinetic dynamometer (Biodex®)	As an objective measure of strength, maximal isokinetic knee extensor strength in the right leg will be measured at speeds of 60 degrees/sec. The left leg will be used if there is a reason not to measure the right leg.
Postural Sway	Center-of-Pressure (COP) trajectory data will be collected using an Advanced Mechanical Incorporated (AMTI) AccuSway biomechanics force platform. Participants will be barefoot in an upright stance with arms raised comfortably at their sides, feet abducted, and heels separated. Four posturographic parameters (maximum antero-posterior and medio-lateral displacement, average sway velocity, and 95% confidence ellipse) and two statistical mechanics measures (stabilogram diffusion analysis and detrended fluctuation analysis) will be calculated to quantify postural sway according to our previously published methods.
Sarcopenia measures	
Grip-strength	As an objective measure of weakness and marker of sarcopenia.[33]
Gait speed	Determined based on 4-meter walk at usual speed as a marker of sarcopenia.[35]
SARC-F	The SARC-F questionnaire is validated to identify adults with sarcopenia and who are at risk for adverse outcomes and may benefit from a physical function intervention. [34]
Whole Body DEXA scan Time:	The appendicular lean muscle mass/height will be calculated based upon a whole-body DEXA scan performed in the Geriatric Research Unit.
Physical Activity Assessments	
Community Healthy Activities Model Program for Seniors (CHAMPS) questionnaire	The CHAMPS questionnaire is a brief valid measure that assesses weekly frequency and duration of various physical activities common to older adults to evaluate the efficacy of behavioral interventions to increase levels of physical activity. Caloric expenditure (MET hours/week) will be reported.[8] 'Low activity' will be defined as <6.2 MET-hours/week of activity. Women with MET hr/week between 6.3 and 11.4 will be classified as low-moderate activity. Since only 23% of incontinent women had >11.4 MET hours/week of physical activity, this level will be defined as high activity.[8]
Barriers to physical activity questionnaire	Questions regarding attitudes towards physical activity considering UI symptoms and perceived barriers will be assessed.
Comprehensive prospective evaluation for physical function limitations	

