The hypothesis for AIM 1 (Primary) will be tested using analysis of covariance (ANCOVA) to compare differences of efficacy of PFME therapy (i.e. % UI episodes/week reduction at week 6) between women with and without functional impairment, adjusted for age, race/ethnicity, and BMI. Differences in least-squares means and associated 95% confidence intervals will be calculated. For Sub-aim 1(a), attitudes (barrier and motivation) towards physical activity will be compared between higher vs. lower physically active women using Chi-Square tests. For Sub-aim 1(b), association between physical activity (lower vs. higher) and UI severity will be tested using logistic regression, adjusting for age, race/ethnicity and BMI. Odds ratio and associated 95% confidence intervals will be calculated. We will also explore the impact of functional impairment on the association by adding an interaction of functional impairment and UI severity. Similar ANCOVA models as for Aim 1 will be used to compare efficacy of PFME therapy between women with and without sarcopenia (AIM 2) and between women with and without mild cognitive impairment (Aim 3).

Potential Pitfalls and Alternative Solutions:

- a) **Recruitment:** Women will be recruited from the community in the catchment area for Wake Forest Baptist Health system, which includes central and western North Carolina and south central Virginia. Last year, we saw 476 women with a urinary incontinence diagnosis. More than 30% of women older than 70 have UI symptoms and an equal number will have functional impairment. Therefore, we do not expect difficulty in recruiting 50 eligible women/year over 24 months. The Wake Forest Sticht Center on Aging has an established database of older volunteers for aging-related research (VITALS database=12,600) that will also be a source of recruitment. If necessary, we may start targeted recruitment to ensure that ~ 50% of potential participants have a SPPB score > 10 and that 50% have scores of ≤ 9 .
- b) **Adherence to PFME therapy:** Participants will receive a calendar with their PFME prescription on it and places on the calendar to document compliance. They will be contacted by study staff every 2 weeks to assess for compliance and to reinforce adherence to therapy. This approach has resulted in good compliance in other trials of elderly adults run by the Sticht Center.

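### Hypothesis 2 calls functional impairment and sarcopenia independent predictors of PFME efficacy, but no planned model contains both

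*Combined protocol and SAP*

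**What the plan says.** Under Objectives, Aim 2, Hypothesis 2 reads: "Functional impairment and sarcopenia status will be independent predictors of efficacy of PFME therapy in a well-characterized cohort of older women with UI". The next sentence narrows this to a prediction that women without functional impairment will improve more.

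The section Analytical Plan & Statistical considerations describes two analyses of efficacy (percentage reduction in weekly UI episodes at week 6) that bear on this:

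- An ANCOVA comparing efficacy "between women with and without functional impairment, adjusted for age, race/ethnicity, and BMI". This is labelled the primary analysis.
- For sarcopenia: "Similar ANCOVA models as for Aim 1 will be used to compare efficacy of PFME therapy between women with and without sarcopenia (AIM 2").

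The only other term involving impairment is its interaction with UI severity in the Sub-aim 1(b) logistic model. That model concerns physical activity, not PFME efficacy, and has no sarcopenia term.

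The aim numbers differ between sections. The impairment comparison belongs to Aim 2 under Objectives but is Aim 1 in the Sample Size Estimate and the Analytical Plan, where Aim 2 means sarcopenia alone. The point holds under either numbering.

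**The concern.** When a hypothesis names two factors together and calls them independent predictors, the natural reading is that each predicts the outcome given the other. Two single-factor models cannot show that. If both are significant, a report could say Hypothesis 2 is supported although one factor carries no information beyond the other.

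The documents give reasons to expect overlap. The expSPPB includes a "4-meter walk to assess usual gait speed" (Study visit 1, section F). The Outcome measures table describes gait speed as "Determined based on 4-meter walk at usual speed as a marker of sarcopenia". The background says sarcopenia may contribute to functional decline, so a sarcopenia-only estimate is a total association that may run through impairment. That is a legitimate quantity, but it does not show independence.

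A joint model also needs one variable per factor, and neither is settled:

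- **Sarcopenia.** Aim 1 says "Sarcopenia status will be determined by the composite of an Appendicular skeletal muscle mass index", usual walking speed below 1 m/s and grip of 20.5 kg or less. Hypothesis 2 says "Sarcopenia with functional impairment will be defined as a grip strength <16 kg or gait speed <1 m/s". Section H says "Sarcopenia will be determined using the following validated questionnaires and objective physical function measures with standard cut-offs" and lists grip, gait speed, SARC-F and DEXA without a rule for combining them.
- **Impairment.** Study Visit 4 contrasts SPPB below 9 with above 10, leaving 9 and 10 unassigned. The Recruitment paragraph under Potential Pitfalls contrasts 9 or less with above 10, leaving 10 unassigned. Neither is stated to define the ANCOVA groups.

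**Working it through.** **1. The plan's own figure.** The Sample Size Estimate gives 50 women per group, 15% drop-off, a 20-point difference, SD 32, two-sided 0.05 and at least 80% power. Completers: 50 × 0.85 = 42.5, taken as 42 per group. Standard error: 32 × √(2/42) = 6.98. Power: Φ(20/6.98 − 1.96) = Φ(0.90) = 81.7%, or 80.8% with the noncentral t. The stated power is reproduced. It applies to the impairment contrast alone.

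**2. What a sarcopenia-only model picks up.** Suppose impairment lowers response by 20 points and sarcopenia has no direct effect. Let *a* and *b* be the prevalence of sarcopenia in impaired and non-impaired women, with equal groups and p = (a + b)/2. Then

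- correlation φ = [(a − b)/2] / √[p(1 − p)]
- apparent sarcopenia difference = 20 × [a/(a + b) − (1 − a)/((1 − a) + (1 − b))]

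For a = 50% and b = 10%: φ = 0.20/√0.21 = 0.44. The apparent difference is 20 × (0.833 − 0.357) = 9.5 points, all of it due to impairment.

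**3. How often this reaches significance.** Simulation: y = 50 − 20 × impaired + N(0, 32), 42 per group, 40,000 data sets per setting, without the three covariates. Data sets with fewer than two sarcopenic women were excluded (5% at 10%/1%, otherwise at most 0.1%). The prevalences are assumptions, since the documents give none.

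| Sarcopenia, impaired/non-impaired | φ | Sarcopenia-only significant | Both single-factor models significant | Both joint terms significant | Impairment power, joint model | 95% CI half-width, joint sarcopenia term (points) |
|---|---|---|---|---|---|---|
| 20%/20% | 0.00 | 5.0% | 4.1% | 4.2% | 80% | 17.5 |
| 30%/20% | 0.12 | 6.2% | 5.2% | 4.1% | 80% | 16.3 |
| 10%/1% | 0.20 | 7.7% | 6.7% | 3.9% | 79% | 31.1 |
| 20%/2% | 0.29 | 11.8% | 10.6% | 3.7% | 77% | 23.4 |
| 30%/5% | 0.33 | 14.4% | 13.1% | 3.5% | 76% | 19.5 |
| 60%/20% | 0.41 | 20.2% | 18.8% | 3.3% | 72% | 15.7 |
| 50%/10% | 0.44 | 22.3% | 20.8% | 3.4% | 71% | 17.0 |
| 80%/20% | 0.60 | 38.1% | 36.3% | 2.9% | 61% | 17.5 |

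The sarcopenia term in the joint model is significant in 4.9–5.2% of data sets throughout.

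**4. Smaller impairment effect.** With 10 points instead of 20, sarcopenia-only significance falls to 5.1, 5.3, 5.7, 6.7, 7.3, 8.8, 9.4 and 13.5% across the same rows. Both single-factor models are significant together in 1.4–5.2% in the first seven rows and 8.9% in the last.

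**5. Reverse case.** With a direct 20-point sarcopenia effect and no direct impairment effect, the impairment-only model is significant in 5.7–37.9% of data sets (last seven rows). The joint impairment term stays at 4.9–5.1%.

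**6. Precision lost by joint adjustment.** The variance of the impairment estimate is multiplied by 1/(1 − φ²). At φ = 0.60 this is 1.5625, so the standard error is 6.98 × 1.25 = 8.73 and power is Φ(20/8.73 − 1.96) = 63%, close to the simulated 61%.

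**7. Why the definition matters.** If the Aim 1 composite requires all three components, every woman who meets it walks below 1 m/s and so also meets the Hypothesis 2 rule. The second group then contains the first, and prevalence and overlap with impairment depend on which rule is used.

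**The case against.** The strongest reply is that the only concrete contrast in Hypothesis 2, impaired against non-impaired women, is tested and powered, so the dispute is over one word. Independent could also mean independent of age, race/ethnicity and BMI. The first part stands: the primary test is sound. The second is possible, but the sentence pairs the two factors, and if the narrower sense is meant the plan should say so.

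Other points also carry weight:

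- The larger error rates depend on assumed overlap and on the design effect of 20 points. At weak overlap or a 10-point effect the problem is small.
- The joint model is weak. If both factors truly had direct 20-point effects, both joint terms would be significant in only about 19–53% of trials across these settings. That is a reason to report intervals, not a reason to infer independence from models that cannot test it.
- If impairment lies on the path from sarcopenia to response, the joint sarcopenia term is a direct effect. The single-factor estimate remains valid for the total association, so both should be reported and labelled.
- The SPPB bands serve a week-12 subset and contingent recruitment, so their gaps are not errors in themselves. The Hypothesis 2 rule may describe a combined phenotype and not sarcopenia alone. Either way, the variables for the efficacy models remain undefined.
- Eligibility after amendment 12 is limited to SPPB of 9 or less. This may serve to balance the groups, but it means the 42/42 split used here is the planned split, not a known one.

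**Conclusion.** The concern holds as a gap between a stated hypothesis and the stated analysis. The plan's models test each factor adjusted for three covariates; none tests either factor given the other. The size is conditional: negligible at correlations up to about 0.2 (sarcopenia-only significance of 5–8% against a nominal 5%) and material at moderate or strong overlap (12–38%), given a 20-point impairment effect, SD 32, 42 completers per group and no direct sarcopenia effect. Prevalence and overlap are assumptions.

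Such a result would not be a false positive for the sarcopenia comparison as planned. It would be false support for the claim of independence. The primary impairment comparison is untouched, so this should be fixed but does not threaten the main result.

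**What to change.** Keep the single-factor week-6 impairment ANCOVA as the primary, powered test. Then:

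1. Pre-specify one secondary ANCOVA of the same outcome with impairment and sarcopenia together, plus age, race/ethnicity and BMI. Report both mutually adjusted differences with 95% confidence intervals, beside the single-factor estimates.
2. Report the impairment-by-sarcopenia cross-tabulation.
3. Before analysis, reconcile the sarcopenia definitions (Aim 1, Hypothesis 2, section H) and state the impairment cut-off, so that each factor is one variable assigned to every woman. Align the aim numbers at the same time.
4. Use the word independent only on the basis of the joint model, read from its intervals. Do not take a non-significant term as no effect.

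The cost is SAP wording and one model on measurements already scheduled at baseline. The real downside is precision. Impairment power in the joint model is about 61–80%, against 81% in the primary test. The half-width for the direct sarcopenia effect is about 16–23 points, and about 31 if sarcopenia is rare (10%/1%). Joint power for a direct 20-point sarcopenia effect is about 25–70%, so the model may leave the question open. Deleting the word independent from Hypothesis 2 is the no-cost alternative.
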